# 7.1.6 Pregnancies

Not applicable for this study.

# 7.1.7 Safety Laboratory Measurements

Not applicable for this study.

## 7.2 Efficacy Assessment

There is no assessment of efficacy in this study.

## 7.3 Immunogenicity Assessment

The measures of immunogenicity used in this study are standard, i.e., widely used and generally recognized as reliable, accurate, and relevant (able to describe the quality and extent of the immune response).

The functional measure of immunogenicity used in this study, the serum bactericidal assay using complement (SBA), is a measure of the ability of antibodies, in concert with complement, to kill meningococci, and is widely used.

For the human SBA (hSBA) the complement is of human origin and generally recognized as the serological correlate of protection.

For the rabbit SBA (rSBA) the complement is derived from baby rabbits.

For the SBA analyses the serum samples of all subjects from visit 5 and visit 6 will be used.

The SBA will be used to measure the induction of functional bactericidal antibodies directed against the capsule polysaccharides of the meningococcal serogroups A, C, W and Y following study vaccination.

The measures of immunogenicity using this assay will be:

- hSBA: the percentages of subjects who achieve hSBA titers  $\geq 8$  and
- rSBA: the percentages of subjects who achieve titers  $\geq 8$  and  $\geq 128$ .
- hSBA and rSBA: GMT's.

Testing will be conducted by a Novartis or designated laboratory in a blinded manner towards the visit.

#### 8.0 STATISTICAL CONSIDERATIONS

# 8.1 Endpoints

# 8.1.1 Primary Endpoint(s)

# 8.1.1.1 Primary Safety Endpoint(s)

Safety of the study vaccine will be assessed in all subjects in terms of the frequency and percentage of reported adverse events (AEs) including:

- Any solicited AEs reported within 30 minutes after each vaccination;
- Solicited local (i.e. erythema, induration and tenderness) and systemic (i.e. change in eating habits, sleepiness, irritability, vomiting, diarrhea, and fever (body temperature ≥ 38°C (100.4°F)) AEs reported from Day 1 to Day 7 after each vaccination;
- All medically-attended unsolicited AEs reported from Day 1 to Visit 6 (24 months of age);
- AEs leading to premature withdrawal reported from Day 1 to Visit 6 (24 months of age);
- SAEs reported from Day 1 to Visit 6 (24 months of age);

# 8.1.1.2 Primary Efficacy Endpoint(s)

Not Applicable.

## 8.1.1.3 Primary Immunogenicity Endpoint(s)

One year after the full vaccination of 4 doses MenACWY (at 2 months, 4 months, 6 months and 12 months of age), establish the persistence by:

- Percentage of subjects with  $hSBA \ge 8$  for each serogroup.
- The percentage of subjects with rSBA  $\geq 8$  and with rSBA  $\geq 128$  for each serogroup.

# 8.1.2 Secondary Endpoint(s)

## 8.1.2.1 Secondary Safety Endpoint(s)

Not applicable

# 8.1.2.2 Secondary Efficacy Endpoint(s)

Not applicable

# 8.1.2.3 Secondary Immunogenicity Endpoint(s)

One month after the full vaccination of 4 doses MenACWY (at 2 months, 4 months, 6 months and 12 months of age), evaluate:

- Percentage of subjects with  $hSBA \ge 8$  for each serogroup
- The percentage of subjects with rSBA  $\geq$  8 and with rSBA  $\geq$  128 for each serogrouo

One year after the full vaccination of 4 doses MenACWY (at 2 months, 4 months, 6 months and 12 months of age), establish the persistence by:

- hSBA GMT for each serogroup
- rSBA GMT for each serogroup

One month after the full vaccination of 4 doses MenACWY (at 2 months, 4 months, 6 months and 12 months of age), evaluate:

- hSBA GMT for each serogroup
- rSBA GMT for each serogroup

## 8.1.3 Exploratory Endpoint(s)

Not Applicable

## 8.1.3.1 Exploratory Safety Endpoint(s)

Not Applicable

## 8.1.3.2 Exploratory Efficacy Endpoint(s)

Not Applicable

## 8.1.3.3 Exploratory Immunogenicity Endpoint(s)

Not Applicable

#### 8.2 Success Criteria

Not Applicable

# 8.2.1 Success Criteria for Primary Objective(s)

Not Applicable

## 8.2.1.1 Success Criteria for Primary Safety Objective(s)

Not Applicable

## 8.2.1.2 Success Criteria for Primary Efficacy Objective(s)

Not Applicable

## 8.2.1.3 Success Criteria for Primary Immunogenicity Objective(s)

Not Applicable

## 8.2.2 Success Criteria for Secondary Objective(s)

Not Applicable

## 8.2.2.1 Success Criteria for Secondary Safety Objective(s)

Not Applicable

# 8.2.2.2 Success Criteria for Secondary Efficacy Objective(s)

Not Applicable

# 8.2.2.3 Success Criteria for Secondary Immunogenicity Objective(s)

Not Applicable

# 8.3 Analysis Sets

#### 8.3.1 All Enrolled Set

All screened subjects who provide informed consent and provide demographic and/or baseline screening assessments and received a Subject ID.

# 8.3.2 All Exposed Set

All subjects in the enrolled set who receive a study vaccination.

#### 8.3.3 Safety Set

# Solicited Safety Set (solicited local and systemic adverse events and other solicited adverse events)

All subjects in the Exposed Set with any solicited adverse event data and/or indicators of solicited adverse events

Solicited Safety Set vaccination 1

All subjects in the Exposed Set with any solicited adverse event data and/or indicators of solicited adverse events from Day 1 of vaccination 1 and subsequent 6 days

Solicited Safety Set vaccination 2

All subjects in the Exposed Set with any solicited adverse event data and/or indicators of solicited adverse events from Day of vaccination 2 and subsequent 6 days

Solicited Safety Set vaccination 3

All subjects in the Exposed Set with any solicited adverse event data and/or indicators of solicited adverse events from Day of vaccination 3 and subsequent 6 days

Solicited Safety Set vaccination 4

All subjects in the Exposed Set with any solicited adverse event data and/or indicators of solicited adverse events from Day of vaccination 4 and subsequent 6 days

## **Unsolicited Safety Set (unsolicited adverse events)**

All subjects in the Exposed Set with unsolicited adverse event data.

#### **Overall Safety Set**

All subjects who are in any of the Solicited Safety Sets and/or Unsolicited Safety Set.

# 8.3.4 Full Analysis Set (FAS) Efficacy/Immunogenicity Set

## **Full Analysis Set Efficacy**

Not Applicable

## **Full Analysis Set Immunogenicity**

All subjects in the All Enrolled Set who, receive at least one study vaccination and provide in treatment immunogenicity.

• FAS hSBA 1 month

All subjects in the Exposed Set who provide evaluable hSBA immunogenicity data at 1 month after last vaccination

• FAS rSBA 1 month

All subjects in the Exposed Set who provide evaluable rSBA immunogenicity data at 1 month after last vaccination

FAS hSBA 1 year

All subjects in the Exposed Set who provide evaluable hSBA immunogenicity data at 1 year after last vaccination

• FAS rSBA 1 year

All subjects in the Exposed Set who provide evaluable rSBA immunogenicity data at 1 year after last vaccination

# 8.3.5 Per Protocol (PP) Set Efficacy/Immunogenicity Set

All subjects in the different FAS populations Immunogenicity who:

 Have no protocol deviations leading to exclusion (see section 8.3.8, Protocol Deviations) as defined prior to analysis.

PPS are subsets of FAS and should be always defined even if the objectives do not require it. PPS sets will be named corresponding to the FAS populations, PPS hSBA 1 month, PPS rSBA 1 month, PPS rSBA 1 wear and PPS rSBA 1 year.

An example for subjects excluded due to other reason than protocol deviations is when subjects withdrew informed consent.

Doc Number: 68901057

# 8.3.6 Other Analysis Sets

Not Applicable

## 8.3.7 Subgroups

Not Applicable

#### **8.3.8** Protocol Deviations

A protocol deviation is any change, divergence, or departure from the study design or procedures of a study protocol. A protocol deviation may be a reason to remove data from an analysis set at the time of analysis. CSR-reportable protocol deviations will be defined as exclusionary from the analysis according to protocol objectives and endpoints, which will be specified in the statistical analysis plan. In some cases exclusion of data may be due to a reason other than a protocol deviation, e.g. early termination.

# 8.4 Statistical Analysis Plan

# 8.4.1 Analysis of Demographic and Baseline Characteristics

Descriptive statistics (mean, standard deviation, median, minimum and maximum) for age, height and weight at enrolment will be calculated. Distributions of subjects by sex and ethnic origin will be summarized.

## 8.4.2 Analysis of Primary Objective(s)

## 8.4.2.1 Analysis of Primary Safety Objective(s)

## 8.4.2.1.1 Analysis of Extent of Exposure

The number of subjects actually receiving the vaccinations will be summarized.

#### 8.4.2.1.2 Analysis of Solicited Local, Systemic and Other Adverse Events

Most solicited adverse events will be summarized according to defined severity grading scales

Frequencies and percentages of subjects experiencing each adverse event will be presented for each symptom severity. Summary tables showing the occurrence of any local or systemic adverse event overall and at each time point will also be presented.

Post-vaccination solicited adverse events reported from 30 minutes, Day 1 to Day 3, Day 4 to Day 7 and Day 1 to Day 7 will be summarized by maximal severity.

The severity of solicited local adverse events, including injection site erythema, injection site induration, injection site tenderness will be categorized as none, 1 to  $\leq$ 25 mm, 26 to  $\leq$ 50 mm, and  $\geq$ 50 mm (severe local reactions).

Injection site pain/tenderness and systemic adverse events (except fever) occurring up to 7 days after each vaccination will be summarized according to "mild", "moderate" or "severe".

Each solicited local and systemic adverse event will also be further summarized as "none" versus "any".

Implausible measurements (for further definition see statistical analysis plan) will be left out of the analysis.

Use of antipyretics and analgesics will be summarized by frequency by type of use (prophylactic versus treatment) and percentage of subjects reporting use. The influence of antipyretics and analgesics use on the occurrence of specific adverse events (e.g., fever, pain) will be assessed.

Body temperature will be categorized as  $<38^{\circ}$ C (no fever),  $38-38.9^{\circ}$ C (Mild),  $39-39.9^{\circ}$ C (Moderate), and  $\ge 40^{\circ}$ C (severe). Body temperature will also be summarized by  $<38^{\circ}$ C (no fever),  $38-38.4^{\circ}$ C,  $38.5-38.9^{\circ}$ C,  $39-39.4^{\circ}$ C,  $39.5-39.9^{\circ}$ C, and  $\ge 40^{\circ}$ C (severe).

## **8.4.2.1.3** Analysis of Unsolicited Adverse Events

This analysis applies to all adverse events occurring during the study, judged either as probably related, possibly related, or not related to vaccination by the investigator, recorded in AE CRF, with a start date on or after the date of first vaccination. AE starting prior to the first vaccination will only be listed. The original verbatim terms used by investigators to identify adverse events in the CRFs will be mapped to preferred terms using the MedDRA dictionary. The adverse events will then be grouped by MedDRA preferred terms into frequency tables according to system organ class.

All reported adverse events, as well as adverse events judged by the investigator as at least possibly related to study vaccine, will be summarized according to system organ class and preferred term within system organ class. These summaries will be presented by vaccination group and by interval of study observation. When an adverse event occurs more than once for a subject, the maximal severity and strongest relationship to the vaccine group will be counted.

Separate summaries will be produced for the following categories:

- Serious adverse events
- Adverse events that are possibly or probably related to vaccine
- Adverse event leading to withdrawal
- Adverse events leading to a medically attended visit

Data listings of all adverse events will be provided by subject. In addition, adverse events in the categories above will be provided as listed data.

## 8.4.2.1.4 Analysis of Safety Laboratory Values

Not Applicable

## 8.4.2.2 Analysis of Primary Efficacy Objective(s)

Not Applicable

# 8.4.2.2.1 Statistical Hypotheses

Not Applicable

## 8.4.2.2.2 Analysis Sets

Not Applicable

## 8.4.2.2.3 Statistical Methods

Not Applicable

## 8.4.2.3 Analysis of Primary Immunogenicity Objective(s)

## 8.4.2.3.1 Statistical Hypotheses

Not Applicable

## 8.4.2.3.2 Analysis Sets

The primary immunogenicity objective will be run with the FAS population, however the analyses will also be run with the PPS population for sensitivity reason.

#### 8.4.2.3.3 Statistical Methods

Binary data

The primary objective of the study is the persistence one year after the complete schedule of 4 vaccinations, expressed as the number and percentage of subjects with hSBA titer  $\geq 8$  or rSBA titer  $\geq 8$  and  $\geq 128$  at Visit 6.

These percentages will be presented along with associated two-sided 95% Clopper-Pearson confidence intervals.

Handling of missing values for Immunogenicity Data

For immunogenicity data, it may be reasonable to consider missing immunogenicity values as missing completely at random, i.e. not informative. Therefore, the analysis will comprise a complete case analysis.

Titers below the limit of detection will be set to half that limit for the purposes of analysis.

# 8.4.3 Analysis of Secondary Objective(s)

# 8.4.3.1 Analysis of Secondary Safety Objective(s)

Not Applicable

## 8.4.3.1.1 Analysis of Extent of Exposure

Not Applicable

## 8.4.3.1.2 Analysis of Solicited Local, Systemic and Other Adverse Events

Not Applicable

#### 8.4.3.1.3 Analysis of Unsolicited Adverse Events

Not Applicable

# 8.4.3.1.4 Statistical Hypotheses

Not Applicable

# 8.4.3.1.5 Analysis Sets

Not Applicable

## 8.4.3.1.6 Statistical Methods

Not Applicable

## 8.4.3.2 Analysis of Secondary Efficacy Objective(s)

# 8.4.3.2.1 Statistical Hypotheses

Not Applicable

## 8.4.3.2.2 Analysis Sets

Not Applicable

#### 8.4.3.2.3 Statistical Methods

Not Applicable

## 8.4.3.3 Analysis of Secondary Immunogenicity Objective(s)

## 8.4.3.3.1 Statistical Hypotheses

Not Applicable

## 8.4.3.3.2 Analysis Sets

The analysis population will be the FAS defined in Section 8.3. Immunogenicity analysis on the Per Protocol Population will also be performed for sensitivity.

#### 8.4.3.3.3 Statistical Methods

Log-normal distributed data

The statistical analyses will be performed on the logarithmically (base 10) transformed values. Individual titers below detection limit will be set to half that limit.

Geometric mean antibody titers (GMT) and GMRs:

The antibody titers will be summarized using GMTs with two-sided 95% confidence intervals. The calculation will be done by an univariate analysis. GMTs and 95%

confidence intervals will be obtained by exponentiation (base 10) of the logarithmically transformed antibody titer and confidence limits. Moreover the geometric mean ratios (GMR) will be provided along with the 2-sided 95% confidence intervals. GMRs will be calculated between visit 6 (one year after full vaccination) and visit 5 (one month after full vaccination).

Median, minimum, and maximum values will be obtained using original titer values.

Binary data

The evaluation at one month after the complete schedule of 4 vaccinations is expressed as the number and percentage of subjects with hSBA titer  $\geq 8$  or rSBA titer  $\geq 8$  and  $\geq 128$  at Visit 5.

These percentages will be presented along with associated two-sided 95% Clopper-Pearson confidence intervals.

## 8.4.4 Analysis of Exploratory Objectives

Not Applicable

## 8.4.4.1 Analysis of Exploratory Safety Objective(s)

Not Applicable

## 8.4.4.2 Analysis of Exploratory Efficacy Objective(s)

Not Applicable

# 8.4.4.3 Analysis of Exploratory Immunogenicity Objective(s)

Not Applicable

# 8.5 Sample Size and Power Considerations of Primary and Secondary Objectives

Approximately 135 subjects will be enrolled in this study providing approximately 100 evaluable subjects, assuming a 25% drop-out. The sample size is based on the number of subjects requested and agreed with South Korean Health Authorities for this persistence study.

With 100 evaluable subjects, the 95% confidence limits of the observed percentages of subjects with hSBA titer  $\geq 8$  or rSBA titer titer  $\geq 8$  or  $\geq 128$  will be as presented in the following table.

Table 8.5-1: Calculated 95% Confidence Interval, Associated With Different Percentages of Observed Percentages of Subjects

Observed percentage	95% confidence interval (Menveo® N=100)
50%	40%- 60%
60%	50%-70%
70%	61%-79%
80%	72%-88%
90%	84%-96%

Dependent on the point estimate, the length of the confidence interval will be 12% - 20%.

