# Primary Endpoint(s): Immunogenicity Endpoint(s).

No specific criteria are established to assess adequacy of the antibody persistence. All analyses will be run descriptively.

- Percentage of subjects with hSBA  $\geq$  8 at Visits 5 and 6
- hSBA GMTs at Visits 5 and 6
- Percentage of subjects with rSBA  $\geq$  8 at Visits 5 and 6
- Percentage of subjects with rSBA  $\geq$  128 at Visits 5 and 6

Name of Sponsor:	Protocol number:	Generic name of study vaccine(s):
Novartis Pharma Services AG	V59_75	MenACWY-CRM (Menveo®) is a Meningococcal (Groups A, C, Y and W-135), Oligosaccharide Diphtheria CRM 197 Conjugate Vaccine.

• rSBA GMTs at Visits 5 and 6

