#### **Statistical Analyses:**

There is no statistical hypothesis associated with the immunogenicity objective. All analyses will be run descriptively.

The primary objective is to evaluate the persistence of the antibody response against N. *meningitidis* serogroups A, C, W and Y at approximately 1 year after completion of a 4-dose infant vaccination. This persistence will be summarized as the percentage of subjects with a titer  $\geq 8$  (hSBA) or with a titer  $\geq 8$  and  $\geq 128$  (rSBA) along with associated two-sided 95% Clopper-Pearson confidence intervals.

The antibody titers will be summarized using GMTs with two-sided 95% confidence intervals constructed by exponentiation (base 10) of the means and confidence limits of the logarithmically transformed (base 10) antibody titer. Moreover the geometric mean ratios (GMR) between visit 6 (1 year after full vaccination) and visit 5 (1 month after full vaccination) will be provided along with the 2-sided 95% confidence intervals.

Approximately 135 subjects will be enrolled in this study providing approximately 100 evaluable subjects, assuming a 25% drop-out. The sample size is based on the number of subjects requested and agreed with South Korean Health Authorities for this persistence

Name of Sponsor:	Protocol number:	Generic name of study vaccine(s):
Novartis Pharma Services AG	V59_75	MenACWY-CRM (Menveo®) is a Meningococcal (Groups A, C, Y and W-135), Oligosaccharide Diphtheria CRM 197 Conjugate Vaccine.

study.

With 100 evaluable subjects, the 95% confidence limits of the observed percentages of subjects with hSBA titer  $\geq$ 8 or rSBA titer titer  $\geq$  8 or  $\geq$ 128 will be as presented in the following table.

Table 4: Calculated 95% Confidence Interval, Associated With Different Observed Percentages of Subjects

Observed percentage	95% confidence interval (Menveo® N=100)
50%	40%- 60%
60%	50%-70%
70%	61%-79%
80%	72%-88%
90%	84%-96%

Dependent on the point estimate, the length of the confidence interval will be 12% - 20%.

The analyses will be done on the Full Analysis Set (FAS population).

Additional details will be described in the statistical analysis plan.

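### The precision table in protocol 8.5 shows normal-approximation limits, but the planned intervals are Clopper-Pearson; the 70%, 80% and 90% rows and the 12% minimum length are off

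*Protocol*

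**What the plan says.** Protocol section 8.5 states the evaluable number: "Approximately 135 subjects will be enrolled in this study providing approximately 100 evaluable subjects, assuming a 25% drop-out". It then gives the precision. The sentence beginning "With 100 evaluable subjects, the 95% confidence limits of the observed percentages of subjects with hSBA titer" goes on to say that the limits "will be as presented in the following table", which is Table 8.5-1. The rows are 50%: 40 to 60; 60%: 50 to 70; 70%: 61 to 79; 80%: 72 to 88; 90%: 84 to 96. Below the table stands "Dependent on the point estimate, the length of the confidence interval will be 12% - 20" percent. Synopsis Table 4 and the sentence under it are the same. Neither place names the interval method behind the table.

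The method for the percentages themselves is named consistently. Protocol 8.4.2.3.3, for the primary percentages at Visit 6, says: "These percentages will be presented along with associated two-sided 95% Clopper-Pearson confidence intervals". The synopsis (Statistical Analyses), protocol 8.4.3.3.3 and SAP sections 11.2 and 11.3 specify the same method.

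On the role of the table, section 8.5 says: "The sample size is based on the number of subjects requested and agreed with South Korean Health Authorities for this persistence study". The synopsis adds, under the primary endpoints: "No specific criteria are established to assess adequacy of the antibody persistence".

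**The concern.** Every printed row is symmetric about its observed percentage: 70 plus or minus 9, 80 plus or minus 8, 90 plus or minus 6. Clopper-Pearson intervals at 70% to 90% with 100 subjects are not symmetric; they reach further towards 50%. The table therefore cannot come from the method that the plan names for the same percentages.

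The study is single-arm and descriptive, so this table is the protocol's only quantitative statement of what the agreed sample size delivers. If it comes from another method, readers are promised somewhat better precision than the report will show, and most of the shift is in the lower limit, which matters most to a reader judging persistence. A result of 90/100 would be reported as 82% to 95%, where the protocol says 84% to 96%, with nothing to explain the difference.

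**Working it through.** **Inputs.** N = 100 and observed 50%, 60%, 70%, 80%, 90% (protocol 8.5). Two-sided 95% level and Clopper-Pearson method (protocol 8.4.2.3.3 and 8.4.3.3.3, synopsis, SAP 11.2 and 11.3).

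**Step 1: reproduce the printed table.** The normal approximation is p ± 1.96 × √(p(1−p)/100). At 90%: √(0.9 × 0.1/100) = 0.03, and 1.96 × 0.03 = 0.0588, giving 84.12 to 95.88, which rounds to the printed 84 to 96.

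| Observed | Normal approximation | Length | Printed |
|---|---|---|---|
| 50% | 40.20 to 59.80 | 19.60 | 40 to 60 |
| 60% | 50.40 to 69.60 | 19.20 | 50 to 70 |
| 70% | 61.02 to 78.98 | 17.96 | 61 to 79 |
| 80% | 72.16 to 87.84 | 15.68 | 72 to 88 |
| 90% | 84.12 to 95.88 | 11.76 | 84 to 96 |

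All five rows are recovered, and the lengths of 11.76 to 19.60 round to the stated 12% to 20%. Adding a continuity correction gives the same rounded limits, but its shortest length is 12.76, so the uncorrected form fits the 12% better. Wilson, Agresti-Coull, Jeffreys and mid-p intervals do not reproduce the 70%, 80% or 90% row.

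**Step 2: apply the stated method.** With x responders of n, the lower limit is the 0.025 quantile of Beta(x, n−x+1) and the upper limit is the 0.975 quantile of Beta(x+1, n−x).

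| Observed | Clopper-Pearson | Length | Whole percent | Printed |
|---|---|---|---|---|
| 50/100 | 39.83 to 60.17 | 20.34 | 40 to 60 | 40 to 60 |
| 60/100 | 49.72 to 69.67 | 19.95 | 50 to 70 | 50 to 70 |
| 70/100 | 60.02 to 78.76 | 18.74 | **60** to 79 | 61 to 79 |
| 80/100 | 70.82 to 87.33 | 16.52 | **71** to **87** | 72 to 88 |
| 90/100 | 82.38 to 95.10 | 12.72 | **82** to **95** | 84 to 96 |

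**Step 3: size of the difference (printed minus Clopper-Pearson, in points).**

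| Observed | Lower limit | Upper limit | Length, printed vs exact |
|---|---|---|---|
| 70% | +1.0 | +0.2 | 18 vs 18.7 |
| 80% | +1.2 | +0.7 | 16 vs 16.5 |
| 90% | +1.6 | +0.9 | 12 vs 12.7 |

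In the 50% and 60% rows no limit differs by more than 0.3 point. Five of the ten printed limits change at whole-percent rounding; in the 70% row only the lower limit does. Over the tabulated range the length runs from 12.7 to 20.3 points, so the minimum should read about 13 and the maximum of 20 stands.

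**Step 4: could a slightly larger N explain it?** 135 × 0.75 = 101.25. With N = 101, Clopper-Pearson gives 60.4 to 79.0 for 71/101, 71.1 to 87.5 for 81/101, and 82.5 to 95.2 (length 12.6) for 91/101. The printed lower limits of 61, 72 and 84 and the 12% minimum are not recovered.

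**The case against.** The strongest counter-argument is about importance. The sample size was not derived from a precision target, there is no hypothesis, success criterion or interim analysis, and the analysis method is stated correctly everywhere, so every reported interval will be exact whatever the table shows. The evaluable number is itself approximate: if N is assumed to lie between 90 and 110, the Clopper-Pearson length at 90% runs from 13.5 to 12.1 points, a spread of 1.4 points, about twice the 0.7-point length error. All of this stands, and it limits the finding to a small correction. It does not remove the mismatch: across that same range the exact lower limits are 70.3 to 71.3 at 80% and 81.9 to 82.8 at 90%, never the printed 72 and 84.

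A second point is that SAP section 5 refers technical details to a separate sample size memo, which is not among the documents and may name the table's method. That the table used the normal approximation is therefore inferred from the numerical match. The mismatch with Clopper-Pearson does not depend on that inference, because the protocol presents the limits without qualification and its readers do not see the memo.

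Third, the full protocol text available is version 1. The listed changes in the later amendments leave section 8.5 alone, so the table is taken as current.

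Finally, labelling the table as a normal approximation would also remove the unexplained inconsistency. It would, but the table would still show limits that the report will not contain.

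**Conclusion.** The concern holds. Three of the five rows and the stated minimum length do not follow from the interval method that the plan specifies. Every printed limit in those rows is too high and every printed length too short, with the largest error 1.6 points, in the lower limit at 90%. The 50% and 60% rows come from the same approximation but agree with the exact values after rounding.

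The conclusion rests on N = 100 as stated and on Clopper-Pearson being the only method named for these percentages. The consequence is confined to the stated precision: no sample size, analysis, analysis set or decision is affected. It is a definite numerical error with limited consequence, and it should be corrected.

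**What to change.** In protocol Table 8.5-1 and synopsis Table 4:

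- Replace three rows: 70%: 60% to 79%; 80%: 71% to 87%; 90%: 82% to 95%. Leave the 50% and 60% rows as they are.
- Restate the interval length as about 13 to 20 percentage points for observed percentages of 50% to 90%, shorter at higher percentages.
- Name the Clopper-Pearson method in the table title.

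Check the sample size memo and align it if it carries the same figures. SAP section 5 refers to protocol 8.5 and needs no figures of its own.

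The cost is three rows, one sentence and a title in two places, with no change to the sample size or the analysis.
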